7.7.3 Other Assessments

The following assessments will be performed:

- Urine drugs of abuse according to the local standard, including (at a minimum, cocaine, tetrahydrocannabinol, amphetamines and opiates), and alcohol screens via urinalysis or a commercially available urine dipstick.
 - During the screening period, urine drugs of abuse, and alcohol screens may not be repeated for eligibility unless the investigator believes that a positive result is possibly attributable to a concomitant medication; a repeat test will be allowed under this circumstance.
- Serology tests (i.e., HIV-1 and HIV-2 antibodies, hepatitis B surface antigen, and HCV antibody, and any confirmatory tests performed at the discretion of the investigator)
- FSH (as needed to confirm postmenopausal status)
- Transvaginal ultrasound
- Cervical screening test (if needed)
- Speculum examination to identify vaginal abnormalities, with a bimanual examination at Screening
- Endometrial biopsy (if needed): any participant experiencing bleeding during the study will undergo a transvaginal ultrasound and possible endometrial biopsy.
- Record prior and concomitant medications (Section 6.7)

7.7.4 Vital Signs

Vital signs assessments will include oral temperature (°C), respiratory rate (breaths per minute), systolic and diastolic blood pressure (mmHg) and pulse rate (beats per minute). Blood pressure and pulse rate will be measured after the participant has been resting quietly in a supine position or in the most recumbent position possible for at least 5 minutes. Any clinically significant abnormal vital sign assessment requires at least one repeat measurement.

Vital signs abnormalities that are considered clinically significant initially and on confirmation, require a participant to be discontinued from the study, require a participant to receive treatment, or require a change or discontinuation from the study product (if applicable) will be recorded as AEs.

7.7.5 Physical Examination

Comprehensive physical examinations (excluding rectal and breast examinations [unless indicated]) will be performed, and abnormal findings will be documented in the participant's eCRF as shown in the schedule of events (Table 1-1). Additional symptom-directed

CONFIDENTIAL

examinations can be performed at all other visits for participants exhibiting signs or reporting symptoms since their last visit.

An abnormal physical examination finding that is considered clinically significant and requires the participant to be discontinued from the study, requires the participant to receive treatment, or requires a change or discontinuation of the study product (if applicable) will be recorded as an AE.

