- b. Complete physical examination at Screening and EOS/ET visit. Additional symptom-directed examinations can be performed at all other visits for participants exhibiting signs or reporting symptoms since their last visit.
- c. The purpose of the speculum examination on Cycle 1 Day 1 is to identify vaginal abnormalities at baseline, to allow differentiation of baseline abnormalities from AEs related to the IVR.
- d. In addition to scheduled transvaginal ultrasounds, any participant experiencing postmenopausal bleeding during study will undergo a transvaginal ultrasound and possible endometrial biopsy as an unscheduled visit, to have this evaluated histologically.
- e. Upon transvaginal ultrasound:
 - if endometrial thickness is ≤ 4.0 mm in a participant without postmenopausal vaginal bleeding, an endometrial biopsy is not indicated for the purposes of screening
 - if endometrial thickness is > 4.0 mm ≤ 6.0 mm in a participant without postmenopausal vaginal bleeding, an acceptable result from an evaluable screening endometrial biopsy, evaluated by a pathologist, is required for inclusion into the study. Tissue must be read as benign, inactive, or atrophic endometrium by at least 1 pathologist
- f. Height will be measured at Screening only.
- g. Serology tests include HIV-1 and HIV-2 antibodies, hepatitis B surface antigen, and HCV antibodies.
- h. Randomization will occur after screening procedures are completed and eligibility is verified.
- i. Participants will self-administer the IVR in the clinical research unit on Day 1 of each cycle. Insertion should take place after the 0-hour PK sample has been collected. At the end of each cycle, participants will remove their own IVR.
- j. In each cycle, investigators will confirm correct placement of the IVR prior to the first postdose PK sample collection.
- k. Repeated blood sampling for PK will be performed on Day 1 of each cycle, with single samples collected on Day 2 (24 hours postdose), Day 3 (48 hours postdose), and on Days 8, 15, and 22 of each cycle.
- l. On Day 1 of each cycle, repeated blood sampling for PK will be performed, with samples collected at the following time points: 0 (within 10 minutes) hours prior to insertion of the IVR, then after insertion of the IVR at 0.5, 1, 2, 4, and 8 hours following insertion. On Day 1 of Cycle 1, baseline sampling will occur predose at -1, -0.5, and 0 (within 10 minutes) hours prior to insertion of the first IVR.

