7.7.2 Laboratory Tests

A certified laboratory will be utilized to process and provide results for the clinical laboratory tests listed in Table 7-1. The baseline laboratory test results for clinical assessment for a particular test will be defined as the last measurement prior to the first administration of study product.

Participants will fast for a minimum of 8 hours prior to clinical laboratory sample collection at screening. For subsequent clinical laboratory sample collections, participants will not be required to be fasted.

During screening, if a participant has an out-of-range value for a clinical laboratory parameter that the investigator believes is not clinically significant or the investigator does not believe is correct (e.g., laboratory or specimen processing error), but the investigator wants to confirm with a repeat laboratory test, a single repeat is allowed to confirm the initial result.

Additional safety laboratory tests may be conducted as needed by the investigator to evaluate participant safety.

CONFIDENTIAL

Table 7-1: Clinical Laboratory Tests

Hematology	Chemistry	Urine Dipstick
Hematocrit	Albumin	Specific gravity
Hemoglobin	Alkaline phosphatase	Ketones
Red blood cell count	Alanine aminotransferase	pH
White blood cell count	Aspartate aminotransferase	Protein
Neutrophils (absolute)	Gamma glutamyl transferase	Blood
Lymphocytes (absolute)	Direct bilirubin	Glucose
Monocytes (absolute)	Total bilirubin	Leukocyte esterase
Basophils (absolute)	Lactate dehydrogenase	Microscopic analysis (performed if blood, leukocytes, or protein are present)
Eosinophils (absolute)	Total protein	Nitrites
Platelet count (estimate not acceptable)	Blood urea nitrogen	
	Creatinine	
	Calcium	
	Phosphate	
	Sodium	
	Potassium	
	Bicarbonate	
	Chloride	
	Glucose ^a	
	Total cholesterol	
	Triglycerides ^a	

a. Fasting, at screening visit

For any laboratory test value outside the reference range that the investigator considers to be clinically significant during the on-study period (i.e., following dose administration), the investigator will:

- Repeat the test to verify the out-of-range value and clinical significance
- Follow the out-of-range value until the value returns to normal or baseline, or until the value is deemed stable and not clinically significant by the investigator
- Record as an AE any laboratory test value that is confirmed by repeat and which:
 - the investigator considers clinically significant

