8 ADVERSE EVENTS

An AE is defined as any untoward medical occurrence in a participant administered a pharmaceutical product during the course of a clinical investigation. An AE can therefore be any unfavorable and unintended sign, symptom, or disease temporally associated with the use of a study drug/product, whether or not thought to be related to the study drug/product.

Participants will be monitored for AEs throughout the study from the time of consent. Treatment-emergent AEs (TEAEs) will be those with an onset after insertion of the first IVR through the follow-up telephone call. Adverse events that are identified at the last assessment visit (or the early termination visit) as specified in the protocol must be recorded on the AE eCRF with the status of the AE noted. All events that are ongoing at this time will be recorded as ongoing on the eCRF. All (both serious and nonserious) AEs must be followed until they are resolved or stabilized, or until reasonable attempts to determine resolution of the event are exhausted. The investigator should use his/her discretion in ordering additional tests as necessary to monitor the resolution of such events.

The procedures specified in Section 8.4 are to be followed for reporting SAEs.

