8.2.2 Intensity

The intensity of an AE will be graded according to the following definitions:

- Grade 1: Mild; the participant experiences awareness of signs or symptoms but these are easily tolerated or managed without specific treatment
- Grade 2: Moderate; the participant experiences discomfort enough to cause interference with usual activity, and/or the condition requires specific treatment
- Grade 3: Severe; the participant is incapacitated with inability to work or do usual activity, and/or the event requires significant treatment measures
- Grade 4: Disabling or with life threatening consequences, urgent intervention indicated
- Grade 5: Death

CONFIDENTIAL

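### Section 7.7.5 sets a narrower trigger for recording a physical examination finding as an AE than Sections 7.7.2, 7.7.4 and 8, so the same finding can be counted or not counted in the primary AE endpoint

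*Combined protocol and SAP*

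**What the plan says.** Section 7.7.5 of the protocol states when an examination finding becomes an AE. The sentence starts "An abnormal physical examination finding that is considered clinically significant and requires the participant to be discontinued from the study" and ends "requires the participant to receive treatment, or requires a change or discontinuation of the study product (if applicable) will be recorded as an AE". The same section also says that "abnormal findings will be documented in the participant's eCRF as shown in the schedule of events", whether or not they are AEs.

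The two parallel rules are built differently. In Section 7.7.2, once a laboratory value has been confirmed by repeat, the first item in a list of alternatives is that "the investigator considers clinically significant" the value. Discontinuation, treatment and product change are further items, joined by *or*. Section 7.7.4 has the same structure: its list opens with "Vital signs abnormalities that are considered clinically significant initially and on confirmation" and continues with the three actions as alternatives.

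Section 8 gives the general definition: "An AE can therefore be any unfavorable and unintended sign, symptom, or disease temporally associated with the use of a study drug/product". It sets no severity or action threshold. Section 8.2.2 describes Grade 1 as "awareness of signs or symptoms but these are easily tolerated or managed without specific treatment", so events that need no treatment are expected among the AEs.

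Section 9.4.1 lists incidence and severity of AEs first among the primary endpoints. Change from baseline in physical examination findings is a separate primary endpoint.

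**The concern.** Three rules that do the same job should have the same logic, and none should be narrower than the definition it serves. Section 7.7.5 is the odd one out. It ties clinical significance to an action, and no text says whether it or Section 8 decides when the two disagree.

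At stake is consistent counting of the first-listed primary endpoint. About two sites are planned. If one follows the specific rule and the other the general definition, they will classify the same finding differently. The difference would fall on findings that need no action, which are likely to be of lower grade, so it could affect both the incidence and the severity table.

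**Working it through.** The documents give no figure that depends on this rule, so there is nothing to reproduce. The check is one of logic.

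**Step 1: does the parsing of 7.7.5 matter?** Let S = clinically significant, D = study discontinuation, T = treatment needed, P = product changed or stopped. The commas allow two readings:

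- Reading A: S and (D or T or P)
- Reading B: (S and D) or T or P

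For the case in question, S is true and D, T and P are all false. Reading A gives false, and so does reading B. Section 7.7.4 has the form S (confirmed) or D or T or P, which gives true. The gap in 7.7.5 does not depend on how the sentence is parsed.

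**Step 2: the same cases under each rule.** Laboratory and vital-sign entries assume that the abnormality was confirmed on repeat.

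| Case | 7.7.2 laboratory | 7.7.4 vital signs | 7.7.5 examination | Section 8 definition |
|---|---|---|---|---|
| Clinically significant, action needed | AE | AE | AE | AE |
| Clinically significant, no action needed | AE | AE | not triggered | AE if an unfavorable, unintended sign |
| Not clinically significant, no action needed | not triggered | not triggered | not triggered | AE if an unfavorable, unintended sign |

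In the second row 7.7.5 departs from its two parallels and from Section 8. In the third row all three specific rules are narrower than Section 8. Copying the *or* logic alone therefore does not bring 7.7.5 fully into line with the general definition.

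**Step 3: what is lost if the finding is not recorded as an AE.** Under Section 9.6, TEAEs are coded by system organ class and preferred term and classified by severity and relationship to treatment. For physical examination, that section promises only that findings at screening and end of treatment are reported and compared. An unrecorded finding therefore gets no MedDRA term, grade or causality assessment. Findings from symptom-directed examinations between those visits are not named in the comparison.

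**Step 4: how far the rule reaches.** Table 1-1 and its footnote b schedule complete examinations at Screening and EOS/ET, so one falls after the first ring is inserted. Examinations at other visits are symptom-directed. The documents give no rate of examination findings without other complaints, so no undercount can be calculated.

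**The case against.** The best defence is that 7.7.5 says when recording is required and never says *only*. Section 7.7.1 refers to Section 8 for AEs, and Section 8 requires AEs identified at the last visit to be recorded. On this view Section 8 covers the untreated finding and nothing is lost. This stands as a reason not to claim that such findings necessarily drop out. It does not remove the inconsistency: a reader at a site can take the specific sentence as the working rule, and nothing says otherwise.

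The second defence is limited reach. Only one complete examination follows insertion, and a participant who prompts a symptom-directed examination by reporting a symptom already has something that Section 8 covers. In the Phase 1 study (Section 2.3.1.2), the frequent TEAEs were mostly complaints a participant would report herself, and no clinically meaningful abnormalities or trends were seen in physical examination findings. Abnormal findings also stay visible in the eCRF and under their own primary endpoint. All of this stands and keeps the point modest, but it does not supply the grade, causality and coding that AE status brings.

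Two stronger readings are tempting and not supported:

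- A reader might infer that every mild examination finding is lost, since Grade 1 includes events managed without treatment. But 7.7.5 sets no grade threshold, Section 8 sets none either, and a mild finding judged clinically significant that leads to discontinuation or a product change meets 7.7.5.
- A reader might infer that speculum and ultrasound findings have no AE rule at all. They have no rule of their own, but Section 8 covers them. Footnote c to Table 1-1 gives the purpose of the Day 1 speculum examination as "to allow differentiation of baseline abnormalities from AEs related to the IVR", which presupposes that such findings can be AEs.

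**Conclusion.** The point holds as an inconsistency between stated rules. Section 7.7.5 is narrower than 7.7.2, 7.7.4 and Section 8 for one defined case: a clinically significant finding, arising after first insertion, that needs no discontinuation, treatment or product change. Its status in the primary AE endpoint depends on which passage a site applies.

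The size is unknown and probably small. A reader might try to quantify it by noting that one woman in an arm of 10 is 1/10, or 10 percentage points, of TEAE incidence. That is true of any single event and says nothing about how often this case will arise.

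The conclusion assumes that sites could apply 7.7.5 literally and that no separate completion guidance already settles the matter. The documents show none. It is worth correcting because it feeds a primary endpoint and the correction is cheap, not because a material bias has been shown.

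**What to change.** Reword the last sentence of Section 7.7.5 with the logic of 7.7.4 and add a sentence on precedence, for example:

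> A physical examination finding is recorded as an AE if the investigator judges it clinically significant, or if it requires study discontinuation, or if it requires treatment, or if it requires a change or discontinuation of study product. These are minimum triggers. The definition in Section 8 prevails, and this section does not restrict AE recording.

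The precedence sentence is needed because the *or* list on its own would remain narrower than Section 8 (third row of the table). The change concerns recording only and leaves clinical management as it is.

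The cost is a short protocol rewording, matching eCRF instructions, and the usual amendment steps. A few more mild AEs may be recorded, so the reported incidence could look slightly less favorable.

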7.7.6 Electrocardiograms

Electrocardiogram assessments will be conducted as a standard check to ensure overall stable health prior to trial entry.

7.7.7 Appropriateness of Safety Assessments

Safety evaluations selected for this study are typical of those for this participant population and utilize widely accepted measures.

7.8 Exploratory Assessments

7.8.1 Usability and Tolerability Questionnaire

A Usability and Tolerability questionnaire (see [Appendix A](#)) will be administered to all participants in accordance with the schedule of events ([Table 1-1](#)).

7.8.2 Vaginal Cytology

Samples for vaginal cytology will be collected at the time points specified in the schedule of events ([Table 1-1](#)) to determine the maturation index. Investigators should collect a swab of the lateral vaginal wall to be submitted for determination of the vaginal maturation index.

The maturation index is determined by categorizing the ratio of the 3 types of vaginal epithelial cell (parabasal, intermediate, and superficial).

7.8.3 Vaginal pH

Vaginal swabs for determination of pH will be collected in accordance with the schedule of events ([Table 1-1](#)). The pH of vaginal secretions will be measured using pH paper. Additional details and instructions will be provided in the SRM.

7.8.4 Most Bothersome Symptom

At the Cycle 1 Day 1 Visit, participants will rate the first 4 items in the list of VVA symptoms in [Table 7-2](#) as either not present (none), mild, moderate, or severe, and will indicate whether vaginal bleeding associated with vaginal activity is present or absent. They will then select 1 of the 5 symptoms as their most bothersome symptom. All 5 symptoms will be evaluated again during later study visits (see [Table 1-1](#)), and the change in severity from baseline will be determined. Changes from baseline in each participant's most bothersome symptom will be evaluated.

CONFIDENTIAL

Table 7-2: Assessment of Most Bothersome Symptom

Symptom	Assessment
Vaginal dryness	None, mild, moderate, or severe
Vaginal and/or vulvar irritation/itching	None, mild, moderate, or severe
Dysuria	None, mild, moderate, or severe
Vaginal pain associated with sexual activity (dyspareunia)	None, mild, moderate, or severe
Vaginal bleeding associated with sexual activity	Presence versus absence

7.8.5 Menopause-specific Quality of Life

Participants will complete the MENQOL questionnaire (see [Appendix B](#)) on Cycle 1 Day 1 and at the end of the study (see [Table 1-1](#)). Developed in 1996, the MENQOL is a self-administered, 29-item questionnaire with 4 domains: vasomotor, physical, psychosocial, and sexual.

Participants record whether they have experienced the listed problems in the past month, and rate the severity on a Likert scale from 0 (Not at all bothered) to 6 (Extremely bothered) ([Hilditch JR, et al., 1996](#); [Lewis JE, et al., 2005](#)).

Assessment of the severity of VMS at baseline and at the end of the study will be based on the relevant questions from MENQOL.

CONFIDENTIAL

8 ADVERSE EVENTS

An AE is defined as any untoward medical occurrence in a participant administered a pharmaceutical product during the course of a clinical investigation. An AE can therefore be any unfavorable and unintended sign, symptom, or disease temporally associated with the use of a study drug/product, whether or not thought to be related to the study drug/product.

Participants will be monitored for AEs throughout the study from the time of consent. Treatment-emergent AEs (TEAEs) will be those with an onset after insertion of the first IVR through the follow-up telephone call. Adverse events that are identified at the last assessment visit (or the early termination visit) as specified in the protocol must be recorded on the AE eCRF with the status of the AE noted. All events that are ongoing at this time will be recorded as ongoing on the eCRF. All (both serious and nonserious) AEs must be followed until they are resolved or stabilized, or until reasonable attempts to determine resolution of the event are exhausted. The investigator should use his/her discretion in ordering additional tests as necessary to monitor the resolution of such events.

The procedures specified in Section 8.4 are to be followed for reporting SAEs.

8.1 Recording Adverse Events

Adverse events are to be recorded on the AE page of the eCRF. The following information will be recorded:

- Assessment of whether or not the AE is an SAE (Section 8.2.1)
- Assessment of AE intensity (Section 8.2.2)
- Assessment of AE relationship to study product (Section 8.2.3)
- Action taken - categorized as dose increased, dose not changed, treatment interrupted, treatment withdrawn, not applicable, or unknown, as applicable
- Outcome - recorded as fatal, not recovered/not resolved, recovered/resolved, recovered/resolved with sequelae, recovering/resolving, or unknown, as applicable

8.2 Assessment of Adverse Events

The investigator will assess each AE for seriousness, intensity, and relationship to study product.

CONFIDENTIAL

8.2.1 Serious Adverse Events

The investigator is responsible for determining whether an AE meets the definition of an SAE. An SAE is any AE occurring from ICF signing through the follow-up telephone call that results in any of the following outcomes:

- Death
- A life-threatening adverse drug experience
- Inpatient hospitalization or prolongation of existing hospitalization
- A persistent or significant disability/incapacity
- A congenital anomaly/birth defect
- An important medical event*

*Important medical events that may not result in death, be life threatening, or require hospitalization may be considered an SAE when, based upon appropriate medical judgment, they may jeopardize the participant and may require medical or surgical intervention to prevent any of the outcomes listed in this definition. Examples of such medical events include allergic bronchospasm requiring intensive treatment in an emergency room or at home, blood dyscrasias or convulsions that do not result in inpatient hospitalization, or the development of drug dependency or drug abuse.

Note: SAEs require immediate reporting to the sponsor and medical monitor. Refer to Section 8.4 for details.

